**Appendix D. Table 2. Phase 1b - Part 4 Dose Optimization: Schedule of Assessments**

Assessments	$\leq$ -D14	W1 a	W2 D1	W3 D1	W4 D1	W5 D1	W6 D1	W7 D1	W8 D1	W9 + D1	EOT	SFU c	LTFU
	DLT evaluation Period												
	Except where otherwise noted these visit pre-dose assessments can be performed up to 24 hours pre-infusion (see also Section 7). All scheduled treatment days have a window of $\pm$ 2 days											$\leq 1$ Wk h	$\pm 2$ D
Informed consent (within 30 days)	X												
Medical, malignancy history	X												
Physical exam b , ECOG	X	pre m	pre m	pre m	pre m	pre m	pre m	pre m	pre m	pre m	X	X m	
Body weight	X	pre	pre	pre	pre	pre	pre	pre	pre	pre Wk 10 + Q2 wks l	X	X	
Vital signs c	X	pre, (1 hr [EOI]), 2 hr, 4 hr	pre	X	X								
Disease assessment (incl. photographs) d	X i								post	post Wk16, 24 +Q12 wks k	X g		
12-lead ECG	X	pre and post j			pre				pre	pre Wk12 + Q4 weeks	X		
QOL by FACT-G, SKINDEX29	X								post	post Wk16, 24 +Q12 wks k	X		
TTI-621 infusion s		X	X	X	X	X	X	X	X	X			
AEs		X	X	X	X	X	X	X	X	X	X	X	X (TEAE)
Prior/concomitant medications	X	X	X	X	X	X	X	X	X	X	X		
Survival Status													X
Subsequent anticancer therapies													X

D = Day; Post = after start of TTI-621 infusion, EOT = end of treatment visit; SFU = safety follow-up visit; LTFU = long term safety follow-up visit; EOI = end of infusion (1 hr)

Assessments	≤ -D14	W1 a	W2 D1	W3 D1	W4 D1	W5 D1	W6 D1	W7 D1	W8 D1	W9 + D1	EOT	SFU c	LTFU	
DLT Evaluation Period														
		Except where otherwise noted the visit pre-dose assessments can be performed up to 24 hours pre-infusion (see also Section 7 ). All scheduled treatment days have a window of ± 2 days										≤1 Wk h	± 2D	Q4 (±1 wk)
Local Laboratory Assessments														
Hepatitis B/C panel	X													
Pregnancy test (women of childbearing potential)	X (serum)				pre (serum or urine)				pre (serum or urine)	pre Wk 12 then Q4 wks (serum or urine)				
Hematology n	X	pre, 1 hr, (EOI), 2 hr, 4 hr D2, D4	pre, 4 hr, (D2 n* if clinically indicated)	pre, 4 hr, (D2 n* if clinically indicated)	pre	pre	pre	pre	pre	pre	X	X		
	WBC with automated 5-part differential, hemoglobin, RBC, absolute reticulocytes, platelets													
Serum chemistries	X	pre	pre	pre	pre				pre	pre Wk 12 then Q4 wks	X	X		
	Alkaline phosphatase, albumin, ALT, AST, bilirubin (direct, indirect, and total), BUN, creatinine, glucose, LDH, total protein, uric acid, and elec troytes (sodium, potassium, calcium, chloride, bicarbonate, phosphorus)													
Coagulation panel	X	pre	pre	pre	pre				pre	pre Wk 12, W16 then Q4 wks p	X			
	Prothrombin time, partial thromboplastin time, INR, fibrinogen													
Urinalysis		pre									X			
	Including color, appearance, specific gravity, pH, glucose, bilirubin, ketones, occult blood, and protein													
D = Day; Post = after start of TTI-621 infusion; EOT = end of treatment visit; SFU = safety follow-up visit; LTFU = long term safety follow-up visit; EOI = end of infusion (1 hr)														

Assessments	$\leq$ -D14	W1 a	W2 D1	W3 D1	W4 D1	W5 D1	W6	W7 D1	W8 D1	W9 + D1	EOT	SFU e	LTFU	
DLT Evaluation Period														
		Except where otherwise noted pre-dose assessments can be performed up to 24 hours pre-infusion (see also Section 7 ). All scheduled treatment days have a window of $\pm 2$ days.										$\leq 1$ Wk h	$\pm 2$ D	Q4 ( $\pm 1$ wk)
Central Laboratory Assessments														
PK o		pre 1 hr (EOI) 2hr, 4hr, D2, D4	pre	pre	pre	pre	pre, 1 hr (EOI) 2 hr, 4 hr D2, D4	pre	pre	pre Wk 9, 10, 11, 12, 13, 14, 15 & 16	X			
ADA		pre			pre				pre	pre Wk 12 then Q4 wks	X	X	X f	
Peripheral Receptor Occupancy (blood) q		pre, 1 hr (EOI)	pre				pre, 1 hr (EOI)	pre		pre Wk 12 and 16				
Tissue for biomarkers r	X								pre	pre Wk 16				

D = Day; Post = after start of TTI-621 infusion; EOT = end of treatment visit; SFU = safety follow-up visit; LTFU = long term safety follow-up visit; O = optional, EOI = end of infusion (1 hr)

## Footnotes

- a Screening laboratories may be used as pre-dose baseline if within 3 days of Day 1
- b Review of systems and physical exam: breast/chest, extremities, head/ears/eyes/nose/throat, lymph nodes, musculoskeletal, pulmonary, skin, height. Symptom driven on all treatment weeks and SFU. Full exam at screening and EOT.
- c Including heart rate, respiratory rate, body temperature.
- d See [Appendix D, Table 3](#) and [Section 7.14.1](#) for further details, including disease assessment scales. mSWAT, CAILS (if applicable) and photographs are required. All response assessments should be performed at the end of the indicated weeks and the time points have a window of  $\pm 1$  week. The subjects enrolled to phase 1b Part 4 cohorts will not require submission of scans for central review in real time but retrospective submissions might be requested by sponsor.
- e If treatment-emergent abnormalities are present at end of treatment, repeat pertinent labs or studies
- f Subjects who are seropositive at end of safety follow-up should be monitored at least quarterly for 1 year post study to assess persistence of antibodies.
- g If not done in prior 8 weeks
- h Within 1 week following the final dose of TTI-621 (or at the time of premature discontinuation of treatment)
- i Within 28 days of planned start of treatment
- j 12-lead ECG within approximately 30 minutes of completion of infusion (i.e., 60–90 minutes after Time 0)
- k Or at the time of observed or suspected clinical progression
- l After Week 8, the weight taken at the prior visit may be used to calculate dose (e.g. weight at Week 8 used for Week 9 dosing)
- m Symptom driven physical examination
- n Hematology: \*The week 2 and week 3 day 2 assessments are only required if clinically indicated in the event that  $\geq$  Grade 4 thrombocytopenia is observed on day 1 or there are any other clinical conditions indicated for a follow-up lab assessment at the investigator discretion. If a priming regimen is required, refer to [Appendix F](#).
- o PK: if a priming regimen is required, refer to [Appendix F](#)
- p Symptom driven coagulation panel from week 16 onward

q Peripheral Receptor Occupancy (blood): if a priming regimen is required, refer to [Appendix F](#)

r Fresh tumor biopsy required if feasible. Peripheral blood is acceptable for subjects with SS. Archival tissue at screening acceptable, if biopsy not feasible.

s For patients who have been given weekly infusion of TTI-621 for more than a year and are receiving clinical benefit (objective response or clinically meaningful long-term stable disease), investigators may exercise their discretion to reduce the dosing frequency from weekly to bi-weekly following the discussion and approval from the sponsor or designees.

### Appendix D. Table 3. Response Assessments by Malignancy Type

Radiographic disease assessments for CTCL and PTCL will be submitted for central review for those subjects enrolled to phase 1b Part 3. The subjects enrolled to phase 1b Part 4 cohorts will not require submission of scans for central review in real time but retrospective submissions might be requested by sponsor.

Central photography will be utilized for CTCL patients for both phase 1b Part 3 and Part 4.

Disease and Assessments	Screening	Wk 8 	Wk 12 	Wk 16 1+	EOT
Lymphoma (including PTCL)					
PET/CT scan (PTCL: local and central review for phase 1b Part 3 only)	X	X		Weeks 16, 24, and every 12 weeks thereafter	X
Spleen assessment	X	X		Weeks 16, 24, and every 12 weeks thereafter	X
Bone marrow biopsy a	X	X		Weeks 16, 24, and every 12 weeks thereafter	X
Cutaneous T-Cell Lymphoma					
Skin assessment (mSWAT and CAILS)	X	X		Weeks 16, 24, and every 12 weeks thereafter	X
Radiographic imaging (central for CTCL for phase 1b Part 3 only) b	X	X		Weeks 16, 24, and every 12 weeks thereafter	X
Photography of disease (central for CTCL for phase 1b Part 3 and Part 4) k	X	X		Weeks 16, 24, and every 12 weeks thereafter	X
Blood assessment (pathology and flow cytometry): local and central (CTCL) for phase 1b Part 3 only c	X	X		Weeks 16, 24, and every 12 weeks thereafter	X
Spleen and liver assessment	X	X		Weeks 16, 24, and every 12 weeks thereafter	X
Acute Leukemia (AML and ALL)					
Bone marrow aspirate or biopsy d	X	X		Weeks 16, 24, and every 12 weeks thereafter	X
Cytogenetic evaluation e	X	X		Weeks 16, 24, and every 12 weeks thereafter	X
Molecular and/or flow cytometric evaluation f	X	X		Weeks 16, 24, and every 12 weeks thereafter	X
Myelodysplastic Syndrome g					
Bone marrow biopsy	X	X		Week 16, 24, and every 12 weeks thereafter	X
Peripheral blood (including blasts)	X	X		Week 16, 24, and every 12 weeks thereafter	X
Cytogenetic evaluation h	X	X		Week 16, 24, and every 12 weeks thereafter	X
MDS/MPN Overlap (including CMML)					

Disease and Assessments	Screening	Wk 8 	Wk 12 	Wk 16  +	EOT
Bone marrow biopsy	X	X		Week 16, 24, and every 12 weeks thereafter	X
Peripheral blood (including blasts and neutrophil precursors)	X	X		Week 16, 24, and every 12 weeks thereafter	X
Spleen and liver assessment	X	X		Week 16, 24, and every 12 weeks thereafter	X
Cytogenetic evaluation h	X	X		Week 16, 24, and every 12 weeks thereafter	X
Myelofibrosis i					
Bone marrow biopsy	X		X	Week 24 and every 12 weeks thereafter	X
Peripheral blood (including immature myeloid cells)	X		X	Week 24 and every 12 weeks thereafter	X
Spleen and liver assessment	X		X	Week 24 and every 12 weeks thereafter	X
Essential Thrombocythemia and Polycythemia Vera (ET, PV) i					
Bone marrow biopsy	X		X	Week 24 and every 12 weeks thereafter	X
Spleen and liver assessment	X		X	Week 24 and every 12 weeks thereafter	X
Small Cell Lung Cancer					
Radiographic imaging j	X	X		Week 16 and every 8 weeks thereafter	X

a A bone marrow biopsy for lymphomas should be completed if clinically indicated.

b Radiographic imaging should only be performed if visceral lesions were identified at screening and to confirm a response after screening and submitted for central review.

c The blood assessment includes Sézary cell counts and/or flow cytometry for CD4/CD8, CD4+ CD7-, or CD4+ CD26- cells. Blood and pathology submitted for central review

d A bone marrow aspirate or biopsy is required to establish CR, CRi, PR or relapse per IWG Criteria (Cheson et al, 2003). A bone marrow evaluation is also required when the peripheral blood has < 10% peripheral leukemic blasts.

e In order to document a cytogenetic complete remission (CRc), reversion to a normal karyotype must occur; cytogenetics not necessary if normal karyotype.

f In the event of a CR, real-time quantitative PCR (RT-PCR) and flow cytometry should be performed to monitor minimal residual disease (MRD) and to document molecular complete remission (CRm); for subjects in CR, consult with Medical Monitor to review specific tests indicated.

g All criteria must be met and documented for a minimum of 4 weeks to define a complete remission, partial remission, or marrow CR.

h At least 20 analyzable metaphases are required to diagnose or exclude the presence of a cytogenetic abnormality; for subjects in CR, consult with Medical Monitor to review specific tests indicated.

i To confirm a response, all criteria must be met and documented for a minimum of 12 weeks; for subjects in CR, consult with Medical Monitor to review specific tests indicated.

j CT scans of the chest, abdomen, and pelvis should be conducted every 8 weeks. CT/MRI of the brain should be performed if abnormal at baseline

k Canfield photography of target lesions should be conducted and submitted for central storage

l All time points are relative to the end of the respective weeks (ie. end of week 8)

## Appendix E. Cockcroft-Gault Equation for Calculating Estimated Creatinine Clearance

Serum creatinine units	Gender	Estimated Creatinine Clearance (mL/min)
mg/dL	Male	$\frac{(140 - \text{subject age [years]}) \times \text{subject weight (kg)}}{72 \times \text{subject serum creatinine (mg/dL)}}$
	Female	$\frac{(140 - \text{subject age [years]}) \times \text{subject weight (kg)} \times 0.85}{72 \times \text{subject serum creatinine (mg/dL)}}$
$\mu\text{M/dL}$	Male	$\frac{(140 - \text{subject age [years]}) \times \text{subject weight (kg)} \times 1.23}{\text{Subject serum creatinine } (\mu\text{M/dL})}$
	Female	$\frac{(140 - \text{subject age [years]}) \times \text{subject weight (kg)} \times 1.04}{\text{Subject serum creatinine } (\mu\text{M/dL})}$

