- alanine aminotransferase (ALT) and aspartate aminotransferase (AST) < 1.5 x ULN or < 3 x ULN with documented liver metastases

7. Adequate renal function, defined as estimated serum creatinine clearance > 30 mL/minute calculated using the Cockcroft-Gault equation (see [Appendix E](#)).
8. Recovery from the toxicities of previous anticancer drugs or radiotherapy to Grade 0 or 1 (or to baseline grade if condition was pre-existing)
9. Commitment from male and female subjects of reproductive potential to use, from the time of screening through 60 days after the last dose of TTI-621, either:
  - one highly effective method of contraception, including hormonal contraceptives (e.g., combined oral contraceptives, patch, vaginal ring, injectables, and implants), intrauterine device (IUD) or intrauterine system (IUS), vasectomy, or tubal ligation

OR

- at least 2 effective methods of contraception, including male condom, female condom, cervical cap, diaphragm, or contraceptive sponge

OR

- abstain from sex during study participation and for 60 days after the last dose of TTI-621

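### Protocol Appendix E labels creatinine per dL in its metric Cockcroft-Gault rows, but the printed factors are per-litre factors, so following the label inflates clearance about 10-fold

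*Protocol*

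**What the plan says.** Inclusion criterion 7 in Protocol Section 4.1, listed under the heading for both phases, reads: "Adequate renal function, defined as estimated serum creatinine clearance > 30 mL/minute calculated using the Cockcroft-Gault equation". It refers the site to Appendix E for the equation.

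Appendix E is a four-row table with a column headed "Serum creatinine units":

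| Unit label | Sex | Formula as printed |
|---|---|---|
| mg/dL | Male | (140 − age) × weight / (72 × creatinine) |
| mg/dL | Female | (140 − age) × weight × 0.85 / (72 × creatinine) |
| µM/dL | Male | (140 − age) × weight × 1.23 / creatinine |
| µM/dL | Female | (140 − age) × weight × 1.04 / creatinine |

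The per-dL label on the metric rows appears three times: in the unit column and in both denominators. In the equation markup a denominator reads "Subject serum creatinine } (\mu\text{M/dL". Nothing else in the protocol or the SAP restates or corrects the unit.

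**The concern.** The table offers two routes to the same quantity, so both should give the same clearance for the same patient. With the printed unit they do not.

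This table is what a site uses to decide whether a subject meets the renal criterion. The criterion covers every cohort, including the higher dose levels of Part 4. Protocol Section 7 has serum chemistries run at local laboratories, and no reporting unit for creatinine is specified, so which rows a site uses depends on its laboratory. The error runs in one direction only: a subject who fails the criterion by the mg/dL rows can pass it by the metric rows.

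**Working it through.** **Inputs from Appendix E:** the constant 72 and the female multiplier 0.85 (mg/dL rows); the factors 1.23 and 1.04 and the label µM/dL (metric rows). **Input from Section 4.1:** the threshold of 30 mL/min.

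**Assumption not in the documents:** the molar mass of creatinine (C4H7N3O), which from atomic weights is 113.12 g/mol. Hence 1 mg/dL = 10 mg/L = 88.4 µmol/L = 8.84 µmol/dL. The label is read literally as micromoles per decilitre.

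**Step 1. What conversion do the printed factors imply?** For the two halves of the table to agree, the number of metric units per 1 mg/dL must be:
- male: 72 × 1.23 = 88.6
- female: 72 × 1.04 / 0.85 = 88.1

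Both match 88.4 (per litre). Neither is near 8.84 (per dL).

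**Step 2. What factor would each unit need?**

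| Unit of creatinine | Male: conversion / 72 | Female: 0.85 × conversion / 72 |
|---|---|---|
| µmol/L | 88.4 / 72 = 1.228 | 0.85 × 88.4 / 72 = 1.044 |
| µmol/dL | 8.84 / 72 = 0.123 | 0.85 × 8.84 / 72 = 0.104 |
| Printed | 1.23 | 1.04 |

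The printed factors are the per-litre factors.

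**Step 3. Does this hang on the exact molar mass?** No. If about 88.4 µmol/dL corresponded to 1 mg/dL, the molar mass would be 1000 µg / 88.4 µmol = 11.3 g/mol, less than a single carbon atom. Letting the conversion run from 88 to 89 µmol/L per mg/dL, the inflation is 88.56/8.8 = 10.06 down to 88.56/8.9 = 9.95 for males, and 88.09/8.8 = 10.01 down to 88.09/8.9 = 9.90 for females.

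**Step 4. Size in individual patients (mL/min).**

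| Patient | Creatinine | mg/dL row | Metric row, per dL as labelled | Metric row, per L |
|---|---|---|---|---|
| Male, 60 y, 70 kg | 1.0 mg/dL | 5600/72 = 77.8 | 5600 × 1.23/8.84 = 779 | 5600 × 1.23/88.4 = 77.9 |
| Male, 60 y, 70 kg | 5.0 mg/dL | 5600/360 = 15.6 | 6888/44.2 = 155.8 | 6888/442 = 15.6 |
| Male, 65 y, 70 kg | 2.5 mg/dL | 5250/180 = 29.2 | 5250 × 1.23/22.1 = 292 | 5250 × 1.23/221 = 29.2 |
| Female, 65 y, 70 kg | 2.5 mg/dL | 5250 × 0.85/180 = 24.8 | 5250 × 1.04/22.1 = 247 | 5250 × 1.04/221 = 24.7 |

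The last three patients fail the criterion by the mg/dL rows and pass it by the metric rows as labelled.

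**Step 5. What does the threshold become under the literal label?** A printed value of 30 corresponds to 30/10.02 = 2.99 mL/min (male) or 30/9.97 = 3.01 mL/min (female) on the mg/dL rows. Almost no one would be excluded.

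**The case against.** The case for treating this as minor has real content.

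- **Only half the table is affected.** The mg/dL rows are sound. A site that enters a µmol/L result directly, ignoring the dL, gets the right answer (77.9 against 77.8 in the first example). The documents do not show that any site converts to the printed unit.
- **The unit is malformed.** µM already means µmol/L, so µM/dL is not a proper concentration, and some readers would recognise a slip.
- **The error often shows itself.** A routine patient comes out at 779 mL/min. A subject whose clearance is 15 to 30 by the mg/dL rows would show roughly 150 to 300.
- **There are partial safeguards.** Creatinine and BUN are collected at screening (Section 7.1), and exclusion criterion 15 bars other significant medical conditions that would compromise safety.
- **No analysis is touched.** Creatinine clearance is not an endpoint (Protocol Section 8.1), is not among the baseline variables in SAP Section 3.2, and does not drive any rule in Protocol Table 6-1.

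These points limit how likely and how wide the harm is. They do not make the table correct. The metric rows were presumably printed so that some sites could use them, and an eligibility formula should not depend on readers disregarding its stated unit. The safeguards do not replace the criterion either: exclusion 15 is a matter of judgement, while the clearance limit is a fixed number. Nor is the error always conspicuous: the subject with 5.0 mg/dL shows 156 mL/min, and higher creatinine values give lower, less remarkable figures. A text-extraction fault is unlikely because the label occurs three times, though the source PDF should be checked.

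**Conclusion.** The concern holds. The unit label and the factors in the metric rows of Appendix E contradict the mg/dL rows of the same table by a factor of about 10, always towards a higher clearance. Followed literally, the metric rows would let through subjects with a clearance anywhere above about 3 mL/min against a stated limit of 30.

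The conclusion rests on the molar mass of creatinine and on a literal reading of the label as micromoles per decilitre. It is confined to the two metric rows and to sites that convert to the printed unit. The effect is on one screening criterion, not on any planned analysis. It should be corrected because that criterion applies to every cohort and the correction is trivial.

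**What to change.** Change the unit of the metric rows in Appendix E to µmol/L in all three places: the unit column and the two denominators. Keep the factors 1.23 and 1.04. The metric rows then reproduce the mg/dL rows to within 0.3% (ratio 1.002 for males, 0.997 for females), and the 30 mL/min threshold is untouched. Keeping the dL label would instead require factors of 0.123 and 0.104, which is the less natural repair.

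The cost is one correction made three times, with no effect on sample size, design or analysis. If enrolment has ended, a short erratum is enough, together with a check of any eligibility decision calculated from the metric rows. That check needs only the recorded screening creatinine, its reporting unit, and age, weight and sex.

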CCI

## **Statistical Analysis Plan**

This document has undergone the following changes:

Version Number	Version Date	Description of Changes
1.0	26JUL2016	Original document
2.0	02NOV2022	Updates made to align with changes made to the protocol, notes-to-file, and Pfizer's recommendations

PPD

## List of Abbreviations

ADA	antidrug antibodies
ADaM	Analysis Dataset Model
AE	adverse event
AML	acute myeloid leukemia
BMI	body mass index
CD47	transmembrane protein and the target of TTI-621
CDISC	Clinical Data Interchange Standards Consortium
CI	confidence interval
CR	complete response
CRF	case report form
CSR	Clinical Study Report
CTCAE	Common Terminology Criteria for Adverse Events
CTCL	cutaneous T-cell lymphoma
DLT	dose-limiting toxicity
DOR	duration of response
ECG	electrocardiogram
ECOG	Eastern Cooperative Oncology Group
HL	Hodgkin lymphoma
IMWG	International Myeloma Working Group
IV	intravenous(ly)
JAMA	Journal of the American Medical Association
LCL	lower confidence limit
MDS	myelodysplastic syndrome
MedDRA	Medical Dictionary for Regulatory Activities
MTD	maximum tolerated dose
NCI	National Cancer Institute
NA	not applicable
NE	not evaluable
ORR	overall response rate
PD	progressive disease
PDX	pharmacodynamics
PET	probability of early termination
PFS	progression-free survival
PK	pharmacokinetics
PR	partial response
PT	preferred term
PTCL	peripheral T-cell lymphoma

RAEB	refractory anemia with excess blasts
RD	recommended dose
SAE	serious adverse event
SAP	Statistical Analysis Plan
sCR	stringent complete response
SRC	safety review committee
SD	stable disease
SDTM	Study Data Tabulation Model
SOC	system organ class
TEAE	treatment-emergent adverse event
TFLs	tables, figures, and listings
TTI-621	investigational product
VGPR	very good partial response
WHODRUG	World Health Organization Drug Dictionary

## **1 Introduction**

The purpose of this Statistical Analysis Plan (SAP) is to describe in detail the statistical summaries to be performed by Sarah Cannon Development Innovations for Pfizer study *TTI-621-01, A Phase 1a/1b Dose Escalation and Expansion Trial of TTI-621, a Novel Biologic Targeting CD47, in Subjects with Relapsed or Refractory Hematologic Malignancies and Selected Solid Tumors*. The scope of this document includes statistical analyses to be prepared for the abbreviated Clinical Study Report (aCSR).

This SAP is based on version 9.0 of Clinical Protocol TTI-621-01 (dated 20 Feb 2019) and version 14.0 of Case Report Form (CRF) TTI-621-01 (dated 17 Apr 2020). If amendments are made to either of these documents, this SAP will be updated as appropriate.

Statistical analyses to be performed by Pfizer Inc. or by vendors other than Sarah Cannon Development Innovations are outside of the current scope of this document. In particular, it is currently planned that analyses of pharmacokinetic/pharmacodynamic (PK/PDx) data will take place outside of Sarah Cannon Development Innovations; the text of the SAP describing these analyses has been provided as-is to Sarah Cannon Development Innovations for inclusion in the SAP.

